2.6 Pre-Treatment Procedures

If the subject is of childbearing potential (i.e. females not post-menopausal or not surgically sterile), they will be asked if they are pregnant, the date of their last menstrual cycle, and perform a urine pregnancy test. At each subsequent treatment, subjects will be asked the date of their last menstrual cycle for pregnancy verification purposes. A urine pregnancy test may also be conducted at the Investigator's discretion at any time during the study. If a urine pregnancy test is conducted, then a negative result must be obtained within 24 hours prior to the treatment.

Urine Pregnancy Test Procedure:

1. A urine sample is tested mid-stream or by cup sample with an indicator stick.
2. Negative results are indicated on the indicator stick.

- Photographs will be taken prior to the first treatment and may be taken prior to each subsequent treatment.

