2.10 Biopsy Portion of the Study

- Subjects may enroll in the biopsy portion of this study. If the subject has signed the biopsy consent form and enrolled, the following will also be performed:
 - Biopsies may be taken from a treated area the day of treatment and/or may be taken 1, 3, 7 (+/- 1 day), 14 (+/- 2 days), 21 (+/- 2 days), and/or 30 days (+/- 3 days) post last treatment. A control will also be taken on the contralateral side of the treatment area.
 - Biopsy subjects may receive up to 6 biopsies.
 - A local anesthetic, such as lidocaine, may be injected to the area prior to biopsy.

- A 2 mm or 3mm punch biopsy (based on Physician assessment) will be taken from the treatment area.
- Sutures may be used to close the incision site.
- The subject may be asked to attend a 1 week (7-14 days) post each biopsy visit to remove the sutures and assess side effects.
- The following post biopsy treatment instructions will be reviewed:
 - Slight redness, initial tenderness to the wound site is normal; however, if you experience more redness, swelling, pain, pus, or drainage contact the study site immediately.
 - If the biopsy site begins to bleed, apply direct pressure for 10-20 minutes. If it continues to bleed, call the study site immediately.
 - Keep the wound dry today and remove bandage in 24 hours and leave off.
 - Avoid hot tubs, pools, and ocean until sutures are removed. Avoid soaking in water until 14 days after your biopsy.
 - When showering, wash carefully and do not scrub or traumatize the treated skin, or allow spray of shower to strike the skin directly. If the skin is treated harshly, this can increase the risk of scarring.
 - After showering, lightly pat dry the wound or let it air dry, then cover the biopsy site with an application of Vaseline (or petroleum jelly) at least 1-2 times daily. Keeping the wound moist reduces infection, minimizes scarring, and prevents crust formation over the wound.
 - Band-Aids (or any generic Adhesive Bandages) may be used for sleeping or in daily routines where the area may be rubbed/irritated. Whenever possible, keep Band-Aid (or generic Adhesive Bandage) off of the area and keep the area moist with Vaseline (or petroleum jelly) as previously described but do not allow drying out and forming a hard scab.

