 - For any wound discomfort, you may take Tylenol as needed, or use cold compresses for up to 20 minutes hourly as needed. If using ice, it should be wrapped in a plastic and then a cloth to avoid burning your skin and wetting your bandage.
 - Avoid picking at the wound site, which increases risk of infection and scarring.
 - In order for the wound to heal properly and not leave bumpy scars, be careful not to overstretch the wound site area. As a wound heals, it will be weaker than the surrounding skin and can even "pop open" the sutures (stitches) if stretched too much. Sport or strenuous exercises that can pull at the wound site are best avoided for at least the next 3 days and up to one week.
 - Return for suture removal within 7 - 14 days as instructed per study protocol. If applied, Steri-strips must be kept dry as they are more likely to separate when wet. Steri-strips will usually fall off by themselves or you may be advised by the study doctor to remove them when the wound healed.
 - ONCE SUTURES ARE OUT: To minimize sore formation and to improve the final appearance of your skin, it is very important to keep the wound site area covered with the Vaseline for the next few days, until there is no more crust forming and the skin has completely healed.
 - Temporary discoloration at the wound site is normal and should gradually fade over the next few months. Please protect newly healed biopsied area with SPF and avoid sunburn.

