2.13 Evaluation Methods

Photographs:

Photographs will be taken at all visits and will be used to assess efficacy and safety of treatment.

Treatment Discomfort/Pain Evaluation:

Subjects will be asked to report the general level of treatment discomfort on a scale of 0 (none) to 10 (maximum intolerable pain) using the universal pain assessment tool (Appendix B)

Subject and Clinician Satisfaction Questionnaire:

The subject will be asked their level of satisfaction using a 6-point Likert scale that ranges from “extremely satisfied” to “extremely unsatisfied.”

Subject Satisfaction	
Rating	Description
6	Extremely Satisfied
5	Satisfied
4	Slightly Satisfied
3	Slightly Unsatisfied
2	Dissatisfied
1	Extremely Unsatisfied

Blinded Evaluation:

Three blinded independent reviewers will perform a photographic evaluation in which they will be asked to identify pre-treatment images when compared to post treatment images. The reviewers will be Board Certified Dermatologist and/or Surgeons and be chosen based on availability and have relevant clinical experience. They will attend a training session prior to grading.

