2.14 Adverse Event Recording

All data captured must be supported by the Investigator's timely assessment and documentation of the adverse event in the case report forms or source documents. All documented adverse events will be reviewed by the Sponsor or designee to determine whether the adverse event meets regulatory reporting requirements and to ensure timely adverse event reporting to meet local and global regulatory requirements. All adverse events must be followed until their resolution.

Adverse Events Pertaining to the SoftWave Device:

Potential adverse effects associated with shock wave treatments include those listed below:

- Transient moderate increase in pain
- Redness and swelling
- Hematoma and petechial hemorrhage
- Headaches and fainting during extracorporeal shock wave treatments
- Short-term hypoesthesia
- Nausea during therapy
- Tingling during therapy

Adverse Events Pertaining to the Marker:

Using a marker has minimal risks and may produce effects on the body such as redness or a rash.

Adverse Events Pertaining to Ultrasound Gel:

The gel is a water-based gel that may be placed on the skin during treatment. No known adverse events are documented. However, an allergic reaction is always possible when placing a topical gel onto the skin. Allergic reaction may include a mild reaction such as skin redness, irritation, or hives.

Biopsies

Complication with biopsies can include pain, redness, swelling, infection, bleeding, scarring and skin texture irregularities.

Lidocaine

You may experience pain and numbness at the site of the injection. You may also experience redness, rash, infection, skin damage or nerve damage at the site of the injection. You may experience temporary loss of sensation and muscle function at the site of injection.

1% lidocaine (Lidocaine) with Epinephrine Injection

Lidocaine with epinephrine contains the preservative sodium metabisulfite which may cause allergic-type reactions including anaphylactic symptoms such as itching, hives, swollen areas of the body, and/or trouble breathing and life-threatening or less severe asthmatic episodes in certain susceptible people.

Other Cautions:

Incomplete response or no response may occur since some subjects may not respond to treatment.

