2.15 Statistical Analysis**2.15.1 Hypothesis**

For this study to be considered a success, the average pain score is acceptable to the Physician as it relates to the type of treatment.

For additional objectives to be considered a success, the following criteria must be met:

- The side effect profile (adverse events) is acceptable to the Physician as it relates to the type of treatment.
- The subject satisfaction rates at the follow up visit will be $\geq 80\%$ (optional).
- Correct identification of pre-treatment images when compared to post treatment (30 and/or 90 day) images will be $\geq 80\%$ (optional).
- Successful collection of biopsies (optional).
- Successful collection of treatment assessment questionnaires (optional).

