13.0 PHOTOGRAPHY

Standardized photographs will be taken of the treatment area. The subject will be asked to remove jewelry, make-up, and lotions prior to each photo session. Photographs will be taken with an appropriate high-resolution digital camera. Camera settings (lighting, distance, background, polarization, etc.) will be reproduced at each visit, so that photographs are suitable for comparison. Photographs will be taken of the treatment area for study purposes. If the subject does not wish to have their photographs taken, they cannot be in the study.

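### Biopsy marks in the photographed area can show reviewers which image is post-treatment, biasing the optional 80% photo-identification criterion upward

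*Combined protocol and SAP*

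**What the plan says.** - **The task.** Under 2.13 Evaluation Methods, three blinded independent reviewers, dermatologists and/or surgeons, are asked to "identify pre-treatment images when compared to post treatment images". The optional criterion in 2.15.1 is "Correct identification of pre-treatment images when compared to post treatment (30 and/or 90 day) images will be" at least 80%.
- **The images.** Section 13.0 states: "Standardized photographs will be taken of the treatment area". Section 2.6 fixes the baseline image: "Photographs will be taken prior to the first treatment". Follow-up images come at 30 and 90 days after the last treatment.
- **The biopsies.** Section 2.10 is optional and has its own consent. A 2 or 3 mm "punch biopsy (based on Physician assessment) will be taken from the treatment area", on the day of treatment and/or at listed days up to day 30 (+/- 3) after the last treatment. A subject may have up to 6, and sutures may be used. It adds: "A control will also be taken on the contralateral side of the treatment area".
- **The marks.** Section 2.10 tells subjects: "Temporary discoloration at the wound site is normal and should gradually fade over the next few months". Section 2.14 warns: "Complication with biopsies can include pain, redness, swelling, infection, bleeding, scarring and skin texture irregularities".
- **The analysis set.** Section 2.15.3 bases efficacy on everyone who receives at least one treatment. It also says these patients are randomized, but the protocol describes no randomization, so I read the set as all treated subjects.

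No section crops or masks biopsy sites, keeps them out of the photographed field, excludes biopsied subjects from the photo review, or reports it by biopsy status.

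**The concern.** The photo review is meant to show whether treatment changes the skin visibly. It can do that only if treatment is the one systematic difference between the two images of a pair. In a biopsied subject there may be a second difference, a punch site or suture mark, and it can appear only in the later image. Blinding the reviewers does not help, because the cue is in the picture, and dermatologists and surgeons are well placed to recognise it.

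A correct pick made from a biopsy mark would be counted as a visible device effect. This is the only evaluation the protocol describes as blinded, and section 2.1 says the imaging is to support additional marketing claims.

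The wording that allows the 30-day visit, the 90-day visit or both to decide adds a smaller problem: the visit with the better result could be chosen afterwards.

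**Working it through.** The plan gives no calculation for the 80% threshold or for the 50 subjects in 2.15.2, so there is no figure to reproduce. The check has two parts.

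**1. Order of events**

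- Baseline image: before the first treatment, so before any study biopsy of the treated area.
- Biopsies of the treated area: from the day of treatment to day 30 (+/- 3) after the last treatment.
- 30-day image: after most of the possible biopsy days. A day-30 biopsy may follow the photograph.
- 90-day image: after every biopsy.
- Discoloration: expected to fade over months, so it can still be present at either follow-up.

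The cue runs in one direction only.

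**2. Size of the effect**

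Inputs from the protocol: 50 subjects (2.15.2) and an 80% threshold (2.15.1), so success is at least 40 of 50.

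Assumptions, because the protocol is silent: images are shown as pairs; each subject gives one result; all 50 are evaluable; a share *f* is biopsied; a fraction *v* of biopsied subjects has a visible mark; reviewers are right with probability *p* when no mark shows and always right when one does.

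- Probability correct in a biopsied subject: *v* + (1 - *v*)*p*
- Expected rate overall: *f*[*v* + (1 - *v*)*p*] + (1 - *f*)*p*. With *p* = 0.5 and *v* = 1 this is 0.5 + 0.5*f*: 60% at *f* = 20%, 70% at 40% and 80% at 60%.
- Chance of success: exact tail of the sum of two binomials, with 50*f* biopsied and 50(1 - *f*) non-biopsied subjects.

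Worked example, *f* = 40%, *v* = 1, *p* = 0.5: 20 subjects are correct for certain, so 20 of the other 30 are needed. P(Bin(30, 0.5) >= 20) = 0.0494.

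No device effect (*p* = 0.5), chance of at least 40 of 50:

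| Biopsied share | All marks visible | 80% visible | 50% visible |
|---|---|---|---|
| 0% | 0.001% | 0.001% | 0.001% |
| 20% | 0.1% | 0.05% | 0.02% |
| 40% | 4.9% | 1.5% | 0.2% |
| 50% | 21% | 5.9% | 0.5% |
| 60% | 59% | 18% | 1.3% |

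True identification rate 70%, below the threshold (*p* = 0.7):

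| Biopsied share | All marks visible | 50% visible |
|---|---|---|
| 0% | 7.9% | 7.9% |
| 20% | 31% | 17% |
| 40% | 73% | 31% |

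*Fewer evaluable pairs.* With *p* = 0.5, *f* = 40% and all marks visible, the chance is 4.9% for 50 pairs, 11.9% for 30 and 19.4% for 20. Without marks it is 0.001%, 0.07% and 0.6%.

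*Better of two visits.* If the guesses at the two visits are independent and every mark is visible at both, the chance is 1 - (1 - P)^2. The 4.9%, 21% and 59% become 9.6%, 38% and 83%. If guesses are positively correlated between visits the rise is smaller, so these act as upper bounds. With no marks the chance is still only 0.002%.

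**The case against.** The strongest reply is that every step is optional or conditional. The criterion, the imaging and the biopsies are all optional, and the schedule in 2.13 marks the follow-up visits as optional too. Biopsies may be taken at a single timepoint, some will be contralateral controls, and 6 is a ceiling. A 2 or 3 mm mark need not be visible: the discoloration is described as temporary, scarring only as a possible complication, and the body site, framing and imaging method shown to reviewers are not stated. With no device effect, false success stays below 5% up to a 40% biopsied share at 50 pairs even if every mark shows, and nothing in the protocol points to a larger share.

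All of that stands as a limit on size. It does not change the direction of the bias, and the protocol sets no cap on the biopsied share. The case of no effect at all is also the mildest one. When the true identification rate is somewhat below 80%, or fewer than 50 pairs are evaluable, a modest share matters more.

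It is also fair to say that the deciding visit, the presentation order and the three-reader rule are separate questions of endpoint definition. They are secondary here and add no weight to this point.

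**Conclusion.** The concern holds. As written, the plan allows biopsy marks to be counted as evidence of a visible device effect, and any such bias is upward. With no device effect and 50 pairs it is small at a low biopsied share, and decisive only when about half or more of the subjects are biopsied and most marks show. With a true rate near the threshold it is material at a 20% share.

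These sizes rest on assumed values for the biopsied share, the visibility of marks and the identification rate without marks, and on paired images with one result per subject. Confidence in the size is therefore moderate. Only the optional photo criterion is affected. The change should be made, but the trial's primary success does not depend on it.

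**What to change.** **Main change, in 2.13 Evaluation Methods and 2.15.1.** Either crop or mask the same region in both images of a pair, so that no biopsy site or suture mark shows; or base the criterion on non-biopsied subjects, written into 2.15.3 as a stated exception to the efficacy population.

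**Secondary, in the same edit.** Name one deciding visit and make the other supportive. Show each pair in random order. State how the three reads become one result per subject. Report the rate with an exact 95% confidence interval against 50%.

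**Cost.** Wording in three sections and some image preparation, with no new visits or reviewers. Cropping hides part of the treated area. Exclusion leaves fewer pairs, but the result stays readable. An observed 80% has these exact (Clopper-Pearson) 95% intervals:

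- 40 of 50: 66% to 90%
- 24 of 30: 61% to 92%
- 16 of 20: 56% to 94%

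All exclude 50%. With 20 unmarked pairs, pure guessing reaches 80% only 0.6% of the time: P(Bin(20, 0.5) >= 16) = 0.0059.

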1.2 Objectives

1. Primary Objective:
 - Collection of Treatment Discomfort/Pain Evaluation
2. Additional Objectives:
 - Evaluation of tissue response through Biopsies at multiple timepoints up to 30 days post treatment (optional):
 - Sample staining as appropriate, such as H&E
 - Nano-string for Gene Expression
 - Device comparison treatment with similar low-intensity shockwave device (optional).
 - Photographic evaluation with Vivosight imaging at the 30 and/or 90 day follow up compared to baseline (optional).
 - Photographic evaluation with 2D and/or 3D imaging at the 30 and/or 90 day follow up compared to baseline (optional).
 - Subject treatment assessment through questionnaires (optional):
 - Subject treatment experience questionnaire
 - Subject follow up questionnaire
 - Subject satisfaction questionnaire
 - Clinician treatment assessment through questionnaires (optional):
 - Clinician treatment questionnaire
 - Clinician satisfaction questionnaire
3. Safety Objectives:
 - Collection of Adverse Events

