2.15.2 Sample Size Rationale

Based on the need for data collected from this study, it was determined that a total of 50 subjects will be required, including departures.

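### The optional photo criterion of 80% correct shows that pre- and post-treatment images can be told apart, not that the skin improved

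*Combined protocol and SAP*

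**What the plan says.** Section 1.2 lists as an additional objective: "Photographic evaluation with 2D and/or 3D imaging at the 30 and/or 90 day follow up compared to baseline (optional"). Section 2.15.1 attaches a success criterion to it: "Correct identification of pre-treatment images when compared to post treatment (30 and/or 90 day) images will be" at least 80%, again marked optional.

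Section 2.13 (Evaluation Methods) describes the task. Of the three blinded reviewers it says that "they will be asked to identify pre-treatment images when compared to post treatment images". The reviewers are trained beforehand. The section does not state how many images are shown at once, whether a reviewer may decline to choose, how three readings become one result, or any rating of better or worse. Sections 2.15.3, 2.15.4 and 2.15.6 do not fill these gaps.

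Section 2.13 also gives the purpose of the images: "Photographs will be taken at all visits and will be used to assess efficacy and safety of treatment". Sections 1.1 and 2.1 say the study is meant to support further marketing claims.

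Section 2.10 allows biopsy subjects up to six biopsies, by 2 mm or 3 mm punch in the treatment area, from the day of treatment to 30 days (± 3) after the last one. A control biopsy is taken on the opposite side. Section 13.0 says the treatment area is what is photographed. Nothing removes biopsied subjects from the photo evaluation.

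**The concern.** Picking the pre-treatment image answers one question: do the two images differ in a way that reveals their order? Efficacy is another question: is the later image better? The plan collects an answer only to the first, yet assigns photographs an efficacy role.

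Two things separate a correct pick from benefit. Some picks are right by guessing, and the threshold makes no allowance for that. Others are right because of a cue unrelated to improvement. The clearest such cue in the plan is a punch-biopsy mark, which can appear only in the later image. Section 2.14 lists scarring and skin texture irregularities among biopsy complications, and the wound instructions in section 2.10 expect discoloration to take months to fade.

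At stake is whether a rate of 80% or more could properly be cited as photographic evidence of benefit. As specified, it could not.

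**Working it through.** **Inputs.** From the plan: a threshold of 80%, three reviewers, and a sample size for which "it was determined that a total of 50 subjects will be required, including departures" (section 2.15.2). With one pair per subject, that is at most 50 pairs per time point. Not in the plan, hence assumed: two images per set, a forced choice, and the rule for combining readings. The 80% has no derivation to reproduce.

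**1. Distinguishable pairs needed.** Let v be the share of pairs with a difference that leads to a correct pick, and g the chance of being right on the rest. Expected share correct = v + g(1 − v), so v = (0.80 − g)/(1 − g).

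- With g = 0.50: v = 0.30/0.50 = 60%.
- In 50 pairs: 30 distinguishable + 20 × 0.5 = 10 guessed correctly = 40, and 40/50 = 80%.
- This holds for pooled readings. It also holds for a majority of three independent guesses, since 3/8 + 1/8 = 0.5.

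**2. Other rules the text would allow.**

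- Declining to choose is allowed and counted as not correct (g = 0): v = 80%.
- All three must be right (g = 1/8): v = 0.675/0.875 = 77.1%.
- Any one of three right is enough (g = 7/8 = 87.5%): v = 0%, because guessing alone exceeds 80%.

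**3. Changes read the wrong way.** Now let d be the share of pairs with a visible difference and m the share of those in which the wrong image is picked. Then 0.80 = d(1 − m) + 0.5(1 − d), so d = 0.30/(0.5 − m).

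- m = 5%: d = 66.7%
- m = 10%: d = 75%
- m = 20%: d = 100%

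**4. Biopsy marks.** Biopsies scheduled up to day 21 precede the nominal 30-day photograph, and all precede the 90-day one. The number of biopsied subjects is not stated. Assume a share b of pairs shows a mark that always gives the order away, and all other pairs are guessed. Expected share correct = 0.5 + b/2:

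- b = 10%: 55%
- b = 20%: 60%
- b = 40%: 70%
- b = 60%: 80%

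Each 10 points of marked pairs thus add 5 points to the rate with no improvement at all. At b = 20%, only 60% − 20% = 40% of pairs need be distinguishable for another reason.

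**5. Observed against expected.** The criterion is a point value, so 80% can be observed when the expected rate is lower. With one result per pair and g = 0.50:

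- 50 pairs (40 needed): probability about 0.00001 at v = 0, 26% at v = 50%, 58% at v = 60%.
- No visible difference, 10 pairs (8 needed): (45 + 10 + 1)/1024 = 5.5%.
- No visible difference, 5 pairs (4 needed): (5 + 1)/32 = 18.8%.

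Exactly 40 of 50 correct has an exact 95% interval of 66.3% to 90.0%. The unrounded limits, converted by v = 2p − 1, give 32.6% to 79.9% of pairs distinguishable.

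**The case against.** The best defence is that little depends on this criterion. It is optional and additional; study success rests on the pain score. Section 2.15.1 never calls a correct pick an improvement, and the efficacy reading is drawn from section 2.13 and the marketing aim. Harm has its own route: adverse events are recorded at each follow-up visit, have their own criterion in section 2.15.1, and are summarised under section 2.15.6. Section 2.3 bars other procedures on the treated area and section 13.0 standardises the photography, which limits unrelated change. All of this stands. It lowers the importance of the point but does not make a correct pick evidence of benefit.

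A reader might infer that any visible change, including worsening or a tan, counts towards success. The documents do not support that. Such a change counts only if the reviewer still names the right image. A reviewer who expects improvement may take the worse-looking image for the pre-treatment one and be scored wrong, so worsening can lower the rate (step 3). A biopsy mark differs because its order is hardly ambiguous.

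A reader might also point to "Hematoma and petechial hemorrhage", listed in section 2.14 as a device effect. The plan does not say that it would last to day 30 or 90, so it is weak support.

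Nor is chance alone a serious explanation at 50 pairs. It matters only with few pairs, which is possible because the photo evaluation is optional and section 2.15.3 also analyses data by device.

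**Conclusion.** The point holds in a limited form. Without any numerical assumption, the criterion measures distinguishability and cannot by itself support a statement that the skin improved. Its size is conditional: about 60% of pairs correctly distinguishable for an expected 80% correct, given two-image forced choice with pooled or majority reading. Under the other rules considered the figure runs from 0% to 80%, so the 60% should not be read as a property of the written plan.

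A reader might go further and conclude that the criterion would be met without any improvement. The wording permits that, but it is not the expected result. On biopsy marks alone it would take visible marks in about 60% of pairs, and the plan does not say how many subjects will have biopsies.

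The primary objective is unaffected. The matter should be settled before grading starts, because the reviewers' first blinded judgements cannot be collected again.

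**What to change.** Amend sections 2.13 (Evaluation Methods) and 2.15.1 as follows.

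- Show each pair in random order without labels. Each of the three reviewers first rates which image looks better, or no difference, and then picks the pre-treatment image. Rating first keeps the rating from being fitted to the pick. The no-difference option applies to the rating only; the pick stays forced, so that 50% remains its chance level.
- Say which visible feature the rating refers to, and how the three readings combine.
- Report the share correct beside 50% with an exact confidence interval, and describe it as distinguishability only.
- Base any efficacy statement on the share of pairs in which the post-treatment image was rated better. Tabulate pairs in which it was rated worse as a safety result. If a threshold is wanted for the share rated better, set it in advance; the 80% does not carry over automatically to a different outcome.
- Leave out pairs with visible biopsy marks, or mask the same area in both images so that the mask is not itself a cue. Decide this before grading and report the number affected.

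The cost is one extra rating per pair: at most 50 × 3 = 150 per time point, by the same reviewers in the same session. Leaving pairs out widens the interval. The share supporting benefit will probably be lower than the share correctly identified.

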1.0 PURPOSE

1.1 Name and Intended Use

The device used in this study is called the SoftWave device.

The intended use of the SoftWave device used in this study is to assess the usability and tissue response to shock wave treatment and to support additional marketing claims.

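### The tissue-response objective is judged a success on collection of biopsies, so meeting the criterion says nothing about tissue response

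*Combined protocol and SAP*

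**What the plan says.** Section 1.1 states the intended use of the device in this study as "to assess the usability and tissue response to shock wave treatment and to support additional marketing claims". Section 1.2 then sets, among the additional objectives, "Evaluation of tissue response through Biopsies at multiple timepoints up to 30 days post treatment (optional"). Two read-outs are named under it: "Sample staining as appropriate, such as H&E" and "Nano-string for Gene Expression".

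Section 2.10 makes the biopsies voluntary, allows up to 6 per subject, lists seven possible timepoints from the day of treatment to day 30, and adds: "A control will also be taken on the contralateral side of the treatment area".

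Section 2.15.1 introduces its list with "For additional objectives to be considered a success, the following criteria must be met". The only item on biopsies is "Successful collection of biopsies (optional"). A parallel item reads "Successful collection of treatment assessment questionnaires (optional"). Two other items in the list depend on a result: subject satisfaction at follow-up of at least 80%, and correct identification of pre-treatment images of at least 80%.

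**The concern.** The objective is to evaluate tissue, but the criterion asks only that tissue be obtained. A null or unfavourable histology or gene-expression finding would therefore meet the criterion exactly as a favourable one would.

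This is more than a missing detail. A rule is stated, and followed as written it returns a verdict unconnected with the question. It matters because section 1.1 names tissue response in the intended use, next to support for marketing claims, and because subjects who join this part accept punch biopsies, for which section 2.14 lists infection, bleeding and scarring among the possible complications. With no contrast specified in advance, a favourable finding could also be picked out after the samples have been read.

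**Working it through.** **1. Objectives against criteria.**

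| Additional objective (1.2) | Criterion (2.15.1) | Depends on the result? |
|---|---|---|
| Tissue response by biopsy | Biopsies collected | No |
| Photographic evaluation | Correct identification ≥ 80% | Yes |
| Subject satisfaction | ≥ 80% | Yes |
| Treatment-assessment questionnaires other than subject satisfaction | Questionnaires collected | No |

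**2. What the biopsy rule can tell us.** Let q be the probability that biopsies are successfully collected. The documents give no value for q and do not define successful collection. Assume that collection does not depend on the tissue effect. Then:

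- P(success | no tissue effect) = q
- P(success | tissue effect) = q
- likelihood ratio = q / q = 1

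With q = 0.8 both probabilities are 0.8; with q = 1 both are 1. The level of q is irrelevant to the conclusion.

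**3. Is a tissue criterion or analysis given elsewhere?**

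- Evaluation Methods (the second section numbered 2.13) covers photographs, pain, satisfaction and blinded photographic review. It has no biopsy scoring, reader or blinding.
- 2.15.2 gives a total of 50 subjects and no number to be biopsied.
- 2.15.3 says that all data will be analysed by device and overall. That is not a comparison of treated with control tissue.
- 2.15.4 restricts its group comparisons to demographic and medical history variables.
- 2.15.6 covers pain and adverse events and rules out statistical comparisons.

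No treated-versus-control analysis appears in this text.

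**4. What the planned samples could support.** There is no figure of the plan's own to reproduce here. The 50 is not tied to the biopsies, and 2.15.2 gives no effect size, SD, rate, alpha, power or dropout fraction.

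*Pairs per subject.* Assume that the cap of 6 counts control biopsies. A separate control for each treated biopsy allows 6 / 2 = 3 pairs. A single control allows 6 − 1 = 5 treated biopsies, all compared with the same control, so the differences are correlated. Neither covers all seven listed timepoints in one subject.

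*Precision.* As an illustration, assume one paired measure, two-sided alpha 0.05 and 80% power, with d = mean paired difference / SD of the differences. By the normal approximation, n = ((1.960 + 0.842) / d)² ≈ 7.85 / d².

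| d | Pairs, normal approximation | Pairs, noncentral t |
|---|---|---|
| 0.3 | 88 | 90 |
| 0.5 | 32 | 34 |
| 0.8 | 13 | 15 |
| 1.0 | 8 | 10 |

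If all 50 subjects were biopsied at one timepoint each, spread evenly over seven, there would be 50 / 7 ≈ 7 pairs per timepoint. The smallest detectable d would be about 1.27 (noncentral t). If all 50 had a pair at the same timepoint it would be about 0.40. The true number biopsied is unstated and could be far below 50.

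**The case against.** The strongest defence is that this objective is optional and additional, that biopsy enrolment is voluntary, and that study success rests on the average pain score alone. This stands, and it limits the weight of the point. It does not repair the rule: optional governs whether biopsies are taken, not how they are judged once taken.

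The list in 2.15.1 can also be read as requiring all its items jointly. Collection would then be necessary rather than sufficient, and the verdict would depend on other results such as image identification. Those might move with a change in the tissue, but still no item refers to a histology or gene-expression finding.

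Four stronger readings are tempting, and the documents do not support them:

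- *Success is virtually certain, or one biopsy is enough.* Successful collection is undefined and could refer to number, adequacy or timepoints. Only independence from the tissue result follows.
- *The biopsies cannot answer the question.* This is true of the criterion, not of the samples. Staining, gene expression and a contralateral control are all planned, so the tissue can be described and compared.
- *All the questionnaires are judged on collection.* Subject satisfaction has its own threshold of at least 80%.
- *A tissue comparison was never planned.* The numbering runs from 2.15.4 to 2.15.6, and the text does not show whether a 2.15.5 existed. One can say only that none appears in the available text.

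**Conclusion.** The point holds for the criterion as written. Success of the biopsy item has a likelihood ratio of 1 for tissue effect against no tissue effect, at any collection rate, so it supports no statement about tissue response. This assumes only that collecting a biopsy does not depend on the effect. If it did, the dependence would reflect how practicable sampling was, not what the read-outs showed. The treatment-assessment questionnaires judged on collection alone have the same defect.

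A reader might infer that the study's overall conclusion is compromised. It is not, because the pain-based success rule does not use the biopsies. The change should be made because tissue response is part of the stated purpose and the data are meant to support claims.

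**What to change.** In 2.15.1, relabel collection of biopsies and of treatment-assessment questionnaires as feasibility counts, reported as number collected out of number planned, and not as success of the objective. Leave the subject-satisfaction criterion as it is.

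Base any statement about tissue response only on an exploratory, descriptive within-subject comparison of treated biopsies with the subject's contralateral control, using the staining and gene-expression read-outs already planned. Give the number of pairs, and 95% confidence intervals for quantitative measures, at the timepoints where pairs exist. State where one control is reused across timepoints. A difference at every timepoint should not be promised, given the cap of 6 biopsies and a control whose timing is unstated. The biopsy days listed in 2.10 and in the schedule table differ (14 in one, 24 in the other) and must be reconciled first.

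The cost is SAP wording and reporting of read-outs already planned, with no added samples. The downsides are that collection alone can no longer be reported as success, and that estimates may be imprecise because the number of biopsied subjects is not stated.
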